7. To evaluate- gastrointestinal transit in Patients With functional constipation and after ingestion of before blue agave Tequilana Weber fructans.

8. Methodology: General Design.

Describes the overall design of the study and, if relevant, specify the following points:

- a) Study design: Describes if it is randomized / non-randomized, controlled, cohort, Blinding type (double-blind, single), type of controls (placebo, active medication), wash period.
- b) Maneuver or intervention description.
- c) Sample size (# of Patients to be included; justify the calculation)
- d) Treatment allocation mechanism (random / open)
- e) Treatment groups and
- f) Duration of Individual follow-up

Study Design

This is a prospective, randomized, controlled and single blind study to determine the phase III efficacy of the blue agave fructans Tequilana Weber intake in subjects with functional constipation.

In order to Achieve so, it is planned to include over 18 years of Patients age Fulfill the WHO as well as inclusion criteria The Rome III criteria for functional constipation. (See table below) 2.

The phase of our study is designated based on article 66 of chapter II "On Pharmacological Research" of the Regulation of the General Law on Health in Research That defines PHASE III studies Follows as: It is the administration of a research drug to large groups of Patients (Usually external), to define ITS therapeutic utility and identification identify adverse reactions, interactions and external factors That May alter the pharmacological effect.

ROME III criteria

To Comply with the presence of symptoms for more than 6 months before diagnosis, Having Said symptoms for at Least 3 consecutive months or not, and:

1. Absence of abdominal pain or discomfort in the last 3 months.
2. Include 2 or more of the following symptoms.
 - Excessive effort in more than 25% of the evacuations.
 - Hard stool or "pellets" in more than 25% of evacuations.
 - Sensation of incomplete evacuation 25% of evacuations.
 - Sensation of blockage or blockage in 25% evacuations.
 - Maneuvers to Facilitate expulsion in 25% of evacuations.
 - Less than 3 evacuations per week.
3. Stool consistency decrease, rarely, without the use of laxatives.
4. Insufficient criteria of IBS.

Patients of the institute will be called after invitations to Participate in Placing a protocol for Patients With constipation. Patients Who Have Not Been registered and meet the inclusion criteria May Also Participate.

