The study to be Carried out will be Explained and read and, where appropriate, the informed consent will be signed by the Patient During the initial visit (Visit 1) of eligibility, Where the subject will be Given 2 questionnaires (see annexes), one They meet to determine if the ROME III criteria for functional constipation (FC) and another to ASSESS if the patient does not meet the criteria for irritable ROME III bowel syndrome (IBS) and a baseline breath test will be performed.

Having met the inclusion criteria, the patient will be EVALUATED by a graduate in nutrition with the objective of Evaluating the fiber intake in the subject's usual diet. The amount of daily fiber intake will be standardized and a diary will be Given to Evaluate Said intake (see annexes) as well as a diary Where the subject will keep a record of his / her evacuations (see annexes).

In Addition, the previous use of fiber supplements and laxatives, which must be suspended at Least 2 months prior to randomization, will be EVALUATED.

The subject will return to a second visit (Visit 2) (Which will depend on Whether the patient is taking laxatives or fiber supplements) for a complete physical evaluation and the fiber intake diary will be Assessed to determine the amount of fiber intake in the diet as well as the diary of evacuations and the SmartPill © will be Given and That way, the patient will return to the hospital to register the data after the capsule Having evacuated.

The patient will return a week later (Visit 3) on a 12 hour fast, the fiber intake and the evacuation diaries will be re-EVALUATED and will be EVALUATED They again by a nutritionist. A new breath test will be Carried out. The subject will be

Asked to complete the SF-36 Quality of Life Questionnaire. A stool sample will be Collected for ITS analysis in Addition to a blood sample for determination of fasting glucose, glycosylated hemoglobin A1c, Insulin and full lipid profile.

The subjects will be randomized to receive one of four treatments That can be Psyllium plantago 15g, blue agave Tequilana Weber fructans at doses of 5, 10g and blue agave Tequilana Weber fructans at a dose of 5 g + 10 g excipient for a concentration of 33 % of blue agave fructans Tequilana Weber.

The randomization will be computer-generated with a participation number and the assignment of the treatment will be consecutive.

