- functional constipation ROME III criteria as
- Subjects ≥55 years with recent colonoscopy (<3 years)

b) Exclusion criteria

- Taking supplements of fiber in the last 2 months
- Stimulant laxatives consumption chronically (Senna, Bisacodyl)
- decompensated comorbidities (example: uncontrolled diabetes mellitus HbA1c > 9%, decompensated Organ failure, decompensated hypertension (untreated or TA > 160 mmHg systolic and 95 mmHg diastolic)

- Using digital maneuvers or enemas to achieve evacuation
- Personal history of active or previous cancer
- abdominal surgery (except appendectomy, cholecystectomy, hysterectomy)
- Presence of alarm data in the last 6 months (trans-rectal bleeding, unexplained weight loss, abdominal pain)
- Use of drugs known promote constipation (opioid derivatives, clacioantagonistas, anticholinergics tricyclic antidepressants type)
- Prostration (immobility or poor mobility)
- Diseases such as untreated hypothyroidism with hormone replacement, and diseases associated with hypercalcemia that promote constipation
- Other causes of secondary constipation
- Meet criteria for constipation predominant irritable bowel
- Pregnancy.

c) Elimination criteria (considering pregnancy if necessary).

- Requiring individuals to withdraw their informed consent
- acute illness (eg appendicitis, medical-surgical requiring hospitalization intervention and follow-up)
- In our study provides no substitute for patients who have completed or prematurely abandoned the study. It is contemplated an analysis by intention to treat and the percentage of losses for each treatment group will be collected, clarifying the reason why the study was abandoned.

10. Methodology: Outcomes and variables

a) Variables / Main outcome measure

b) Variables / secondary endpoints measured

b) frequency measurements,

c) Criteria for success and failure, and if necessary

d) Strategy statistical analysis.

Where applicable should be specified and substantiated techniques, equipment and / or instruments to be used in the measurement (this includes mechanical / electronic / cyber special equipment, evaluation forms, questionnaires, matching tables, etc.), indicating the validity criteria , reproducibility and quality controls that are the same.

main outcome variable:

Effect of supplementation of fructans Tequilana Weber blue agave in increasing at least one complete evacuation from basal spontaneous.

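### The gain of one evacuation from baseline depends on each patient's starting rate, which entry leaves wide open, yet no between-arm analysis of the main outcome is specified to adjust for it

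*Combined protocol and SAP*

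**What the plan says.** Section 8 (Study Design) sets the order of events. Rome III status is established by questionnaire: "During the initial visit (Visit 1) of eligibility, Where the subject will be Given 2 questionnaires". The criteria ask for onset more than 6 months earlier and "Having Said symptoms for at Least 3 consecutive months or not". Under the second criterion the rule is "Include 2 or more of the following symptoms", with six symptoms listed; fewer than three evacuations a week is one of them.

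Once the inclusion criteria are met, the protocol says: "The amount of daily fiber intake will be standardized and a diary will be Given to Evaluate Said intake". An evacuation diary is issued at the same point. Fibre supplements and laxatives are products "which must be suspended at Least 2 months prior to randomization", and the date of Visit 2 is one "Which will depend on Whether the patient is taking laxatives or fiber supplements". The evacuation diary is assessed at Visit 2. At Visit 3, a week later, "the fiber intake and the evacuation diaries will be re-EVALUATED", and randomisation follows. Neither section 8 nor the selection criteria in section 9 says what diary result confirms or ends eligibility.

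Section 10 gives the main outcome as "Effect of supplementation of fructans Tequilana Weber blue agave in increasing at least one complete evacuation from basal spontaneous", without naming a time window. The statistical analysis plan under Data analysis, item a, compares arms by ANOVA or Kruskal-Wallis for continuous variables. It adds an ANCOVA for variables that might influence the response, without listing them or saying which outcome it serves.

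**The concern.** Entry and outcome are measured on different scales. Entry is a symptom count that can be met by straining and hard stools at a normal frequency. The outcome is a gain in complete spontaneous evacuations over the patient's own baseline. Nothing narrows the baseline rate between the two, because the run-in diary is read but triggers no stated decision.

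This matters because a rule based on a gain of one is not equally easy at every starting rate. Counts vary more when they are higher, so a patient with a high rate passes by chance more often. A patient whose run-in week happened to be low also passes more easily, through regression to the mean. In arms of 15, a few patients more or fewer at one end of the range shift the observed response rate for reasons unrelated to treatment. An unadjusted comparison leaves this variation in the result, although the diary that could remove much of it is already being kept.

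**Working it through.** **1. Inputs.** From the documents: the outcome is a gain of at least one complete spontaneous evacuation (section 10); 15 patients per arm in four arms (section 8); a 15-day averaging window, stated only for secondary variables I and II (section 10). The main outcome has no window, so 15 days and one week are both shown. Assumed: evacuations follow a Poisson distribution with the same rate before and during treatment (no effect), and starting rates run from 1 to 7 per week. The documents give no distribution of baseline rates.

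The plan gives no figure for response by chance, so there is none to reproduce. Its sample size of 15 per arm is taken as stated.

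**2. Chance of a gain of one per week with no effect.** The difference of two independent Poisson counts follows a Skellam distribution.

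- 15-day windows: a gain of 1 per week is 15/7 = 2.14 evacuations, so a whole-number difference of at least 3 is needed. The mean count per window is rate × 15/7.
- One-week windows: a difference of at least 1 is needed. The mean count is the weekly rate.

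| Starting rate per week | 15-day windows | One-week windows |
|---|---|---|
| 1 | 10.8% | 34.6% |
| 7 | 32.3% | 44.6% |

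The dependence on the starting rate appears under both windows. It spans about 22 points with 15-day windows and 10 points with one-week windows.

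**3. What chance imbalance does with 15 per arm.** Suppose, for illustration, that one arm has 10 patients at 1 per week and 5 at 7 per week, and another arm has the reverse. Neither treatment has any effect.

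- 15-day windows: (10 × 10.8 + 5 × 32.3)/15 = 18.0% against (5 × 10.8 + 10 × 32.3)/15 = 25.1%, a spurious difference of about 7 points.
- One-week windows: (10 × 34.6 + 5 × 44.6)/15 = 37.9% against (5 × 34.6 + 10 × 44.6)/15 = 41.3%, about 3 points.

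In general, the difference in mean starting rate between two arms of 15 has a standard error of √(2/15) = 0.37 baseline standard deviations. Imbalances of that order are routine at this size.

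**4. What the written analysis does about it.** ANOVA and Kruskal-Wallis contain no baseline term. Defining the outcome as a change from baseline is not an adjustment: table 2 is computed on change and still depends on the starting rate. The ANCOVA could carry the baseline rate, but as written it does not commit to doing so. It is also a method for continuous outcomes, whereas a gain of at least one reads as a yes/no result.

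**5. What adjustment gains.** Take the weekly rate as continuous, with equal variances before and during treatment and a correlation ρ between them (not given in the documents). Relative to an unadjusted analysis of change, ANCOVA multiplies the variance by (1 − ρ²)/(2(1 − ρ)) = (1 + ρ)/2. For assumed ρ of 0.3, 0.5 and 0.7 this is 0.65, 0.75 and 0.85. It never exceeds 1, apart from the single degree of freedom spent on the covariate.

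**The case against.** The strongest reply is that the diary is not ignored. It is reviewed twice before randomisation, the outcome is already a change from baseline, and an ANCOVA is planned. All three are true. What is missing is a consequence for the diary review and a named covariate for the ANCOVA, so the gap is one of specification. The flow chart and the annexes with the questionnaires and diaries are not available here, so a rule stated there cannot be excluded.

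It can also be said that randomisation balances baseline rates in expectation, so the unadjusted tests are not biased. That stands. The case for adjustment is precision and protection against chance imbalance.

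A reader might infer more: that patients who are no longer constipated will be randomised in numbers, and that this pushes the trial towards finding agave fructans similar to psyllium. The documents do not support that strength. They give no rate of improvement during run-in. Stopping laxatives or fibre would, if anything, tend to worsen constipation, so only diet standardisation or natural fluctuation fits that account. Normal total frequency does not mean little room to gain, because the Rome III item counts all evacuations and the outcome counts complete spontaneous ones. A patient who qualifies through incomplete evacuation may have few of the latter. The direction is not one-sided either: patients who respond alike in every arm shrink a true difference, which would help a similarity claim but work against the superiority that the hypothesis also allows.

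**Conclusion.** The point holds as a gap in the analysis plan. Entry leaves the baseline rate of complete spontaneous evacuations unrestricted, the main outcome is sensitive to that rate, and no between-arm analysis of the main outcome is committed to adjusting for it.

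The size is illustrative. Between 1 and 7 evacuations per week, the chance response triples on 15-day windows (11% to 32%) and rises more modestly on one-week windows (35% to 45%). A one-third against two-thirds imbalance in arms of 15 then produces a spurious difference of roughly 3 to 7 points. These figures rest on Poisson counts, no treatment effect and assumed starting rates. Real diaries may be more or less variable than Poisson, and patients with scarcely any complete evacuations at baseline may dominate, which would narrow the range.

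That patients with little room to gain dilute a true difference remains possible, but the documents do not allow it to be quantified, and covariate adjustment would not reverse it.

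**What to change.** In Data analysis, item a, name the run-in weekly rate of complete spontaneous evacuations as a prespecified covariate in the between-arm analysis of the main outcome:

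- **Continuous form:** ANCOVA on the on-treatment weekly rate, with treatment arm and run-in rate as terms.
- **Responder form:** a baseline-adjusted model for a gain of at least one, such as logistic regression on arm and run-in rate, reported as a standardised difference in response proportions. With 15 per arm, limit the model to this one covariate and state in advance the fallback if it does not converge.
- **Definitions:** state which diary days form the run-in rate and which form the on-treatment rate, identically for all arms, since the main outcome currently gives no window.

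This costs no extra data or visits. The diary is already kept through run-in, and the outcome cannot be scored without a baseline rate of complete spontaneous evacuations. The price is one degree of freedom and a few lines of text.

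Whether the run-in diary should also decide who is randomised is a separate trade-off for the sponsor. It would add run-in failures and would have to be reconciled with the Rome III entry criteria. No threshold is proposed here. The protocol should at least say what, if anything, follows from the diary reviews at Visits 2 and 3.

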The initial treatment of Patients with Functional constipation is based on fiber. There are multiple fiber products in the market, which are Promoted as a supplement for constipation without any scientific evidence to support ITS use. Furthermore, the tolerability of These compounds limits long-term Their use in esta patient population. Scientific evidence is required to support the effectiveness in the use of These fiber supplements in Patients With functional constipation.

6. Justification

There are multiple fibers are in the market That Promoted as a beneficial supplement for Patients With constipation, DESPITE esta, there is not enough scientific evidence derived from randomized and controlled studies to support ITS use. THEREFORE, it is Necessary to Provide evidence to support the use of blue agave fructans Tequilana Weber in Patients With functional constipation.

7A. hypothesis

Defined as a verifiable statement About the relationship Between a variable-dependent and an independent variable. (Remember That the concepts of "null hypothesis", "alternate hypothesis" are related to the statistical analysis So They Should not be included in this item)

General Hypothesis:

Plantago Psyllium When Compared With, the blue agave fructans Weber Tequilana have a like effect or are more effective in Improving functional constipation in adult patients.

Objectives

PRIMARY

1. To Evaluate the efficacy of the blue agave fructans Tequilana Weber in Patients With functional constipation.

SECONDARY

1. To compare the efficacy and tolerability of 5 and 10g doses of blue agave fructans Tequilana Weber in Patients With functional constipation.
2. To Evaluate the impact of the consumption of blue agave fructans Tequilana Weber on the quality of life of the subjects WHO ingest it by Applying the quality of life questionnaire SF-36.
3. To determine the impact of the blue agave fructans of Weber Tequilana intake in the fasting glucose, glycosylated hemoglobin A1c and the lipid profile (metabolic profile) of the subjects WHO ingest it.
4. To Evaluate the presence of short chain fatty acids (butyrate) before vs after the treatment with blue agave fructans Tequilana Weber.
5. To determine the impact of the ingestion of blue agave fructans Tequilana Weber in the microbiota before vs after ingestion.
6. Evaluate to the tolerance to the ingestion of blue agave fructans Weber Tequilana through the use of breath test.

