The product will be supplied in identical bottles With the same amount of powder in a container That will only be identifiable With the name of the protocol as well as the patient's number.

The patient will be provided with a measuring spoon to administer the amount of product Necessary for each of the doses (5, 10 and 15g respectively) or with envelopes Containing the exact Amounts Weighed.

The patient will be instructed to keep a diary of the diet, of the evacuations and a sheet to ASSESS adverse effects. The subject will return (Visit 4) at the end of a month \pm 5 days on a 12 hour fast and Their adherence will be Assessed by product weight in the container subtracting the number of grams required daily ACCORDING TO the assignment of treatment.

The fiber intake diaries will be EVALUATED again by the nutritionist, the evacuation will Also be EVALUATED diary. A medical evaluation will be Carried out That includes questioning and physical evaluation. Subsequently, a blood sample will be to determine fasting glucose Obtained, glycosylated hemoglobin A1c, insulin and lipid profile and a full sample of excrement will be Obtained and SmartPill® will be Given.

The patient will Continue with the supplement in the same container and will be scheduled for a month later. In the end-of-treatment visit visit (visit 5), the fiber will be EVALUATED journals consumption again by a nutritionist and the evacuation will be EVALUATED diary as well.

A medical evaluation will be Carried out That includes questioning and physical evaluation and Their adherence will be Assessed by weighing the product in the container, subtracting the number of grams That it requires daily ACCORDING to the treatment assignment or delivery by the patient of the empty envelopes used.

Subsequently, a blood sample will be to determine fasting glucose Obtained, glycosylated hemoglobin A1c, insulin and lipid profile and a full sample will be Collected stool and breath test at the end will be Carried out.

For end of the visit, Which Will Be Carried out one month after stopping the treatment, the evacuation will be EVALUATED diary and a stool sample will be Collected and with it the intervention in the part of the study will end. Total The follow-up duration for each patient will be 3 months, enough time to observe and compare the effect of the fibers to be used. It is Important to mention That in recent studies Carried out by the same team and with blue agave Tequilana Weber fructans,

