effects on intestinal transit Have Been observed from the first week of intake, in fact this is one of the Reasons to focus the study on functional constipation and intestinal transit.

Breath test:

A breath test will be Carried out in order to measure hydrogen and methane Concentrations previousle Exhaled In Patients randomized in visits 1 and 5.

In order to carry out the breath test gas chromatography equipment will be used, brand Quintron Breath Tracker.

For That, The Patients will be Asked:

- Not to take antibiotics prior weeks At least to the test.
- Stop the intake of food rich in fibers and starches 24 h before the test.
- Not to take alcohol, or smoke
- Have a minimum of 8 hours fasting
- Perform oral hygiene before starting the test and during the performance of measurements.

This test lasts 3 hours, during which the patient can not leave the laboratory facilities motility, can not speak too much or sleep. Exhaled air samples are taken every 15 minutes during this period.

SmartPill®:

[figure not shown]
SmartPill® test will be conducted on visits 2 and 4.

colonoscopy:

Colonoscopy study is a tool which will be subject to scrutiny patients ≥ 55 years with newly diagnosed constipation or those where changes in bowel habits observed in this age group. This fundamental objective, rule out potentially serious diseases and not to delay the diagnosis of these during the research study. one colonoscopic study all patients who have constipation and any of the following characteristics will be used:

1. Diagnosis of constipation less than 1 year
2. Subjects ≥ 55 years who do not have colonoscopic evaluation in the last 3 years prior to study entry
3. Chronic but with alarm data (: Unexplained weight loss, recent transrectal bleeding < 6 months, recent changes in the defecation pattern example) Constipation

Study Flow Chart

Patients include:

Studies with fiber supplements (Psyllium, Plums⁸) Have included 25 to 30 patients per group to find differences between groups.

In total it is planned to include 60 patients randomized as follows: 15 patients receive fructans blue agave Tequilana Weber dose of 5 g, 15 patients received the dose of 10 g, 15 patients received the dose of 5g of agave fructans blue Tequilana Weber + 10 g excipient and 15 patients received 15 g plantago psyllium.

9. Methodology Selection Criteria

a) Inclusion criteria (consider not participating in other research and contraception if necessary)

- Patients over 18 years old.

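### Secondary objective 2 needs an SF-36 score after treatment, but the visit text schedules the SF-36 only at Visit 3, before randomisation

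*Combined protocol and SAP*

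**What the plan says.** The Objectives section sets, as secondary objective 2, an evaluation of the impact of fructan intake on "quality of life of the subjects WHO ingest it by Applying the quality of life questionnaire SF-36".

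Section 8 (Methodology: General Design) describes the visits in order. At Visit 3 the subject is "Asked to complete the SF-36 Quality of Life Questionnaire", and stool and fasting blood samples are collected. The next paragraph states that "The subjects will be randomized to receive one of four treatments". Supply of the product is described after that.

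The same section then gives the later visits:

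- **Visit 4**, about one month into treatment: adherence, diaries, medical evaluation and blood; "a full sample of excrement will be Obtained"; and the SmartPill is given.
- **Visit 5**, end of treatment: diaries, medical evaluation, adherence and blood, and then a "full sample will be Collected stool and breath test at the end will be Carried out".
- **Final visit**, one month after treatment stops: the evacuation diary is reviewed, and "a stool sample will be Collected and with it the intervention in the part of the study will end".

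Section 10 lists five secondary variables: stool form, stool frequency, butyrate, microbiota, and glucose with HbA1c. The Statistical analysis plan (Data analysis, part a) provides a comparison of baseline with later values within groups, a comparison between groups, and an ANCOVA described in general terms.

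**The concern.** An effect of treatment on quality of life can only be judged from a score taken after treatment has begun. In the visit text, the only SF-36 score is taken before anyone is allocated or receives product. The within-group comparison would then have no second value. The between-group comparison would set pre-randomisation scores against each other, and any difference there is chance imbalance, not a treatment effect.

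At stake is one named secondary objective. The loss would also be permanent, because a questionnaire not given at the end-of-treatment visit cannot be recovered later.

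**Working it through.** No figure in the plan is in dispute. The check sets the objectives beside the visit schedule.

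**Step 1. Visits after treatment starts.** Section 8 names Visit 4, Visit 5 and the final visit, so there are 3. That Visit 3 comes before treatment is inferred from the order of the text, and no product is supplied earlier.

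**Step 2. Scheduled measurements for secondary objectives 2 to 7 at those visits.**

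| Objective | Measure | Visit 4 | Visit 5 | Final | Count |
|---|---|---|---|---|---|
| 2 Quality of life | SF-36 | no | no | no | 0 of 3 |
| 3 Metabolic profile | Blood | yes | yes | no | 2 of 3 |
| 4 Butyrate, 5 microbiota | Stool | yes | yes | yes | 3 of 3 |
| 6 Tolerance | Breath test | no | yes | no | 1 of 3 |
| 7 Transit | SmartPill | yes | no | no | 1 of 3 |

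Every measure behind objectives 3 to 7 has at least one later visit. The SF-36 has none.

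**Step 3. Whether another part of the plan supplies the missing visit.**

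- The separate Breath test and SmartPill paragraphs in section 8 restate the visits for those two tests. There is no such paragraph for the SF-36.
- Section 10 has no quality-of-life variable. Lipids, breath test and transit are missing from that list too, but each has a later measurement in section 8. The SF-36 has neither.
- The PAC-QOL appears in the abbreviation list, and a paper on its development is in the citations, but no visit is given for it.
- The medical evaluations at Visits 4 and 5 include questioning. It is paired with a physical evaluation and names no instrument, whereas Visit 3 names the SF-36 outright.

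**Step 4. Size.** Section 8 states "In total it is planned to include 60 patients randomized as follows", with four arms of 15: 4 × 15 = 60. Under the visit text, 0 of 60 would have an SF-36 score after treatment starts.

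**Step 5. Cost of one added assessment at Visit 5.** At most 60 questionnaires. With the 20% loss assumed in the sample size section, 60 × (1 − 0.20) = 48.

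**The case against.** The strongest reply is that the schedule may be complete in a place that cannot be seen here. Section 8 has a heading, "Study Flow Chart", whose content is not in the text available, and the annexes are not there either. Material lost in this way is not missing from the plan, and either source could show a later SF-36. This stands, and it limits the finding to the visit text.

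The visit text is also imperfect evidence of absence. It names no visit for returning the adverse-effect sheet. It places a breath test at Visits 1, 3 and 5, while the Breath test paragraph gives only Visits 1 and 5. The wording of objective 2 presupposes a score after intake, and the generic tests in the analysis plan would fit one. An omitted line is therefore more likely than a deliberate baseline-only design. This also stands, and it is why the point is classed as an internal inconsistency and not as a design choice.

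A reader might infer that, even with a later SF-36 in the flow chart, the time point for analysis would remain undefined because section 10 is silent. That goes too far. A flow chart entry would supply the time point, and section 10 omits other measures as well. What would remain open is which SF-36 score is to be analysed.

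The reply does not remove the gap in the instructions that can be read: staff following the visit text have no direction to repeat the questionnaire.

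**Conclusion.** The point holds as an inconsistency between secondary objective 2 and the visit text of section 8. The text gives one SF-36 assessment before randomisation and 0 of 3 possible ones afterwards. Followed as written, it leaves objective 2 without data on a treatment effect in any of the 60 planned participants.

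This rests on two assumptions: that Visit 3 precedes treatment, as the order of the text implies, and that the flow chart and annexes add no later SF-36. The second could not be checked. A reader might therefore conclude that the trial never measures quality of life after treatment. The documents do not support that; they show only that the visit text does not schedule it.

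The point concerns one of seven secondary objectives and leaves the primary outcome untouched. It should be corrected, because the remedy is small and a missed assessment cannot be recovered.

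**What to change.** First check the flow chart and the annexes.

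- **If they show no later SF-36:** add the questionnaire to the Visit 5 procedures in section 8. List it in section 10 as a secondary variable, naming the score to be analysed. Compare the arms at Visit 5, preferably adjusting for the Visit 3 score through the ANCOVA that the analysis plan already foresees.
- **If they do show one:** add that visit to the section 8 text, and enter the SF-36 in section 10 with the same time point and the score to be analysed.

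In the first case the cost is one questionnaire per participant at an existing visit, one line in the variable list and one sentence in the analysis plan. In the second case it is text alone. Neither needs a new visit or sample.
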